**A. Day 7-10 Follow-Up**

(Phone Call or visit at investigator's discretion)

- Subjects will be asked if they have experienced any untoward medical occurrences since the study procedure. If so, these events will be recorded on the Adverse Event form.
- Symptom and rhythm assessment.

**B. Three-Month Follow-up ( $\pm$  2 weeks)**

The following assessments/procedures will be performed:

- Diagnostic 12-lead ECG
- 72-hr ambulatory continuous ECG monitor (Holter) or CIED interrogation 72 hours prior to visit, as applicable
- EQ-5D and AFEQT Quality of Life survey
- Symptom and rhythm assessment
- Concomitant anti-arrhythmic medications
- Adverse event documentation

**C. Six-Month Follow-up ( $\pm$  2 weeks)**

The following assessments/procedures will be performed:

- Diagnostic 12-lead ECG
- 72-hr ambulatory continuous ECG monitor (Holter) or CIED interrogation 72 hours prior to visit, as applicable
- EQ-5D and AFEQT Quality of Life survey
- Symptom and rhythm assessment
- Concomitant anti-arrhythmic medications
- Adverse event documentation

**D. Twelve-Month Follow-up ( $\pm$  4 weeks)**

The following assessments/procedures will be performed:

- Diagnostic 12-lead ECG
- 72-hr ambulatory continuous ECG monitor (Holter) or CIED interrogation 72 hours prior to visit, as applicable
- EQ-5D and AFEQT Quality of Life survey
- Symptom and rhythm assessment
- EHRA class assessment
- Concomitant anti-arrhythmic medications
- Adverse event documentation

#### E. *Additional Follow-up*

Subjects will be asked to complete the EQ-5D survey monthly, starting at 1 month post-procedure through the 12-month follow up period. The frequency of survey completion may be changed if inadequate patient compliance is observed.

#### F. *Unscheduled Follow-up Visit*

The following assessments/procedures may include:

- Diagnostic 12-lead ECG
- 72-hr ambulatory continuous ECG monitor (Holter) or CIED interrogation 72 hours prior to visit, as applicable
- EQ-5D and AFEQT Quality of Life survey
- Symptom and rhythm assessment
- Concomitant anti-arrhythmic medications
- Adverse event documentation

### 10 ADVERSE EVENTS

At enrollment, time of procedure, and at each post-procedure visit the subject will be evaluated for any complications or adverse event. The Investigator will be required to provide the Sponsor with any information concerning any findings that suggest any adverse events/complications pertinent to the investigation. All AEs occurring during the study will be recorded on the appropriate e-CRFs.

Subjects will be carefully monitored during the study for possible AEs. Any AE observed will be fully investigated by the Investigator and classified in line with the definitions below. All adverse events will be followed until resolution or until the Investigator judges the outcome to be chronic or stable.

#### 10.1 DEFINITIONS

Adverse events will be reported and classified by the Investigator using the specific signs, symptoms or abnormal laboratory values, or medical diagnosis if no signs, symptoms or abnormal laboratory values can be identified. The Investigator will classify the adverse events based on the definitions as follows (EN ISO/FDIS 14155:2010):

- **Adverse Event (AE)** - Any untoward medical occurrence, unintended disease or injury or any untoward clinical signs (including an abnormal laboratory finding) in subjects, users or other persons

whether or not related to the investigational medical device.

NOTE 1: This includes events related to the procedures involved.

NOTE 2: For users or other persons this is restricted to events related to the investigational medical device.

- **Serious Adverse Event (SAE)** - Adverse Event that
  - Led to death
  - Led to a serious deterioration in the health of the subject that either:
    - resulted in a life-threatening illness or injury\*, or
      - resulted in a permanent impairment of a body structure or a body function, or
      - required in-patient hospitalization or prolongation of existing hospitalization, or
      - resulted in medical or surgical intervention to prevent life threatening illness or injury or permanent impairment to a body structure or a body function\*\*.
    - Led to fetal distress, fetal death or congenital abnormality or birth defect

NOTE 1:

\* In this context, the term refers to an event in which the subject was at immediate risk of death at the time of the event; it does NOT refer to an event that might have caused death if it were more severe.

\*\* For example, if the occurrence of a "catheter insertion site hematoma" or an "AV fistula" requires a blood transfusion and/or surgical repair, it should be considered a serious adverse event.

NOTE 2:

- Preplanned hospitalizations for pre-existing condition, or a procedure required by the protocol, without a serious deterioration in health, is not considered to be a serious adverse event.
- Emergency room visits that do not result in hospitalization (i.e., an overnight stay) should be evaluated for one of the other serious outcomes to determine if they qualify as SAEs.
- **Unanticipated Adverse Device Effect (UADE)** - Serious adverse device effect which by its nature, incidence, severity or outcome has not been identified in the current version of the risk analysis report.

## 10.2 ADVERSE EVENT EVALUATION AND REPORTING

- ***Relatedness***

The investigator will assess each adverse event for its relationship to the study device, and whether it was anticipated in the protocol. The determination of the level of relatedness of the adverse event to the study device or procedure will be made according to the definitions below

- Device Related: The adverse event was directly and clearly related to the device or procedure
- Not Device Related
- Unknown

Adverse events that are serious and/or unanticipated will be reviewed immediately by the AEP Medical Monitor and will also be reviewed by the Clinical Event Committee (CEC).

- ***AE Reporting***

Conditions or diseases which are pre-existing and chronic should not be recorded as adverse events (e.g. AF recurrence). Changes in a chronic condition or disease that are consistent with natural disease progression are NOT considered adverse events. Pre-existing conditions or diseases should be documented as part of the subject's medical history.

Elective or pre-planned treatments for atrial fibrillation (e.g. scheduled re-ablation or cardioversion) which are part of the subject's scheduled treatment plan should not be considered adverse events. However, any events related to a procedure (including re-do procedures) or the patient's underlying atrial fibrillation which were not expected or indicate a worsening of condition should be reported as adverse events. (example: procedure-related perforation or cardiac tamponade).

Every effort should be made to report the underlying condition or final diagnosis for the event. The adverse event should be recorded in standard medical terminology rather than the subject's own words when possible. Signs and symptoms that are considered unrelated to an encountered condition or disease should be recorded as individual adverse events (e.g. if congestive heart failure and severe headache are observed at the same time, each event should be recorded as an individual adverse event). In contrast, adverse events that occur secondary to other events (e.g. sequelae), if clearly identifiable, should

be identified by the primary cause (example: bradycardia → dizziness → fainting; the primary adverse event is bradycardia).

- **SAE Reporting**

All serious adverse events should be phoned / faxed / e-mailed to Abbott EP. within 24 hours of learning of an event. The following information will be collected and recorded as appropriate.

- Nature of adverse event
- Date of onset of adverse event
- Date of resolution of adverse event, if applicable
- Statement as to why it is considered unanticipated, if applicable
- Statement as to why it is considered serious, if applicable
- Statement as to the degree to which it is considered device related, and why
- Results of any diagnostic tests that were performed
- Description of any treatment administered

It is the responsibility of each Investigator to report all Serious Adverse Events and/or Serious Adverse Device Effects to the Ethics Committee, according to national regulations and Ethics Committee requirements.

Abbott EP will assure that the Authorized Representative will report all Serious Adverse Events to the Competent Authorities in accordance with European Medical Devices directives and all applicable national regulations.

Any protocol modifications deemed necessary by this review will be reported to the EC and, for sites located outside of Europe, to the applicable Ministry of Health.

### 10.3 ANTICIPATED ADVERSE EVENTS

**Table 8 – Anticipated Adverse Events**

Description	Description
Discomfort due to insertion/removal of vascular sheaths beyond what is normally observed	Ventricular arrhythmia requiring defibrillation
Hemorrhage and/or hematoma at sheath insertion requiring evacuation or transfusion	Cardiac tamponade due to perforation
Extremity weakness, swelling, and/or pain	
Discomfort and/or damage to the skin, muscles, or nerves due to remaining in a supine position for an extended period of time.	Nerve injury (diaphragmatic paralysis, pyloric spasm, gastric hypomotility)
Complete AV block	Air embolism

Nausea /vomiting	Allergic reaction
Headache different from baseline	Endocarditis
Hypertension >180 mm Hg systolic (repeated measures)	Esophageal-atria fistula
Hypotension <80 mm Hg systolic (repeated measures)	Hemothorax
Brief "black out" periods	Pericarditis
Shortness of breath/Dyspnea	Pseudo aneurysm
Feeling of chest pain, skipped beats, and/or rapid heart rate different from baseline	Pulmonary vein stenosis
Damage to skin from prolonged exposure to x-rays	Radiation injury
New arrhythmias (not previously documented)	Renal failure form IV contrast
Arterial injury requiring intervention	Respiratory failure
Thromboembolism	Stroke/TIA
Local/systemic infection	Valvular damage
Pneumothorax	Pleural effusion
AV fistula	Pulmonary edema
Thrombophlebitis	Anemia requiring transfusion
Pulmonary embolism	Vasovagal reaction
Myocardial infarction	New pericardial effusion >1 cm
Discomfort and/or damage to the skin, muscles, or nerves due to percutaneous access in excess of usual	Death (must be reported within the regulation of serious adverse events)
Left heart access via trans-septal puncture has known potential adverse events of: cardiac perforation, cardiac tamponade, and embolic events*.	

\* Literature reviews have demonstrated that the risk of such events are <1%. Mullins, Charles E. "Trans-septal left heart catheterization: Experience with a new technique in 520 pediatric and adult subjects." *Pediatric Cardiology*, v. 4, pgs. 239-246 (1983).

#### 10.4 DEVICE DEFICIENCIES AND MALFUNCTIONS

Investigators must report all possible device deficiencies or malfunctions associated with the device per institutional standard practice and regulations. This includes unexpected outcomes or device deficiencies that might have led to a serious adverse event if a) suitable action had not been taken or b) intervention had not been made or c) if circumstances had been less fortunate.

- **Definitions**

- Device deficiency - inadequacy of a medical device related to its identity, quality, durability, reliability, safety or performance, such as malfunction, misuse or use error and inadequate labeling (EN ISO/FDIS 14155:2010).
- Malfunction - failure of an investigational medical device to perform in accordance with its intended purpose when used in

FIRMAP AF  
Amendment 1  
Date: 15-December 2015

accordance with the instructions for use (EN ISO/FDIS  
14155:2010).

## **11 INVESTIGATOR REQUIREMENTS**

### **11.1 PROTOCOL ADHERENCE**

Each Investigator must adhere to the protocol as detailed in this document and agree that the Sponsor must approve any change to the protocol before seeking approval from the EC or CA. Each Investigator will be responsible for enrolling only those subjects who have met all of the protocol inclusion criteria and none of the exclusion criteria.

### **11.2 ELECTRONIC CASE REPORT FORMS AND DATA CAPTURE SYSTEM**

Data collection will involve the use of the Electronic Data Capture (EDC) system, to which only authorized personnel will have access. Electronic case report forms will be used to capture study data in an EDC system. Entering of eCRFs should be handled in accordance with instructions from the Sponsor or Sponsor representative. All eCRFs must be completed by qualified study center personnel. Each Investigator is responsible for ensuring that accurate data are entered into the EDC system in a timely manner.

The Investigator or designee will be responsible for reviewing eCRFs, resolving data queries generated by the Sponsor via the system, providing missing or corrected data, approving all changes performed on the subject data, and endorsing these data within the EDC system. This approval method will include applying an electronic signature, a uniquely assigned user name, and a password that together will represent a traditional handwritten signature.

Queries may be issued electronically to the study site and answered electronically by that site's personnel. The identifying information (assigned user name, date, and time) for both the originator of the query and the originator of the data change (if applicable) will be collected.

### **11.3 SOURCE DOCUMENT MAINTENANCE**

Source documents may include, but are not limited to, study progress notes, study- or subject-specific e-mail correspondence, computer printouts, laboratory data, and recorded data from automated instruments. The original signed ICF for each participating subject shall be filed with records kept by the Investigator. All documents produced in this study will be maintained by the Investigator and made available for inspection by the Sponsor or Sponsor representative and applicable regulatory authorities.

### **11.4 STUDY MONITORING REQUIREMENTS**

The Sponsor or Sponsor representative will conduct site visits to inspect study data, subjects' medical records, and eCRFs in accordance with current ICH E6 Good Clinical Practice (GCP) guidelines, and the respective United

States or foreign regulations and guidelines, as applicable. The Sponsor or Sponsor representative will also be able to review query status remotely, which may warrant additional communication with the Investigator and the study site's personnel. The Investigator will make available to the Sponsor, or Sponsor representative, source documents, signed ICFs, and all other study-related documents. The Investigator will allow the Sponsor or Sponsor representative and applicable regulatory authorities to inspect facilities and records relevant to this study.

#### 11.5 STUDY COMPLETION

The Sponsor requires the following data and materials before a study can be considered complete or terminated, including, but not limited to:

- Laboratory findings, clinical data, and all special test results from screening through FU
- eCRFs properly completed by appropriate study personnel and signed and dated by the Investigator within the EDC system. This approval method will include applying an electronic signature, a uniquely assigned user name, and a password that together will represent a traditional handwritten signature.
- Copies of complete device accountability records, if applicable
- Copies of all or CA approvals and acknowledgements
- A summary of the study prepared by the Investigator (an EC or CA summary letter is acceptable)

## 12 STUDY MANAGEMENT

Study management will occur in accordance with ISO 14155, (Clinical investigation of medical devices for human subjects – Good clinical practices), the Declaration of Helsinki, the applicable national regulations and Institutional research policies and procedures. Several key components of study management are discussed separately below.

### 12.1 EC OR COMPETENT AUTHORITY APPROVAL

The EC or CA must approve the protocol or amended protocol (if applicable) and the corresponding ICF before the study may be initiated; any recruiting materials before use; and subsequent amended protocols and corresponding ICFs before instituting amendment-specified changes to the study, unless required for subject safety.

The Investigator is responsible for informing the EC or CA of any changes made to the protocol, and to advise the EC or CA, at least once a year, about the progress of the study. The Investigator (or Sponsor, if applicable) is also responsible for notifying the EC or CA of any significant AEs that occur during the study according to local EC or CA requirements.

- **Study Registration**

The study will be registered with [www.clinicaltrials.gov](http://www.clinicaltrials.gov) in accordance with the Declaration of Helsinki.

### 12.2 MONITORING

The study will be monitored periodically at each enrolling site at not less than 3-month intervals for the purposes of

- Verifying compliance to the protocol and applicable regulations,
- Verifying case report form data to original entries in source files,
- Abbott EP employees or representatives will monitor the study according to company standard operating procedures.

### 12.3 STUDY AUDITS

The Sponsor and representatives of regulatory health authorities are permitted to inspect the study documents (protocol, case report forms, study-related medical records, study correspondence with EC and sponsor, etc.). In addition to ongoing monitoring of the study, GCP audits by the

Sponsor or its representatives are also permitted. All attempts will be made to preserve subject confidentiality.

#### 12.4 PROTOCOL DEVIATIONS

A protocol deviation is defined as any event where the clinical investigator or site personnel did not conduct the study according to the protocol.

Investigators can only initiate deviations from the protocol where necessary to protect the life or physical well being of a subject, i.e., in an emergency. Protocol deviations shall be reported to the Sponsor regardless of whether medically justifiable, pre-approved by the Sponsor, or taken to protect the subject in an emergency. Subject-specific deviations will be reported on the eCRF. Non-subject specific deviations, (e.g., unauthorized use of a study device by a physician who has not signed an investigator agreement, etc.), will also need to be reported to the Sponsor. All deviations, regardless of major / minor or pre-approved, will be reported on the eCRF. Investigators will also adhere to procedures for reporting study deviations to their EC in accordance with their specific EC reporting policies and procedures.

Regulations require that investigators maintain accurate, complete and current records, including documents showing the dates of and reasons for each deviation from the protocol.

- **Definitions**

For reporting purposes, the Sponsor classifies study deviations as major or minor:

- Major deviation: Any deviation from subject inclusion and exclusion criteria; subject informed consent procedures (e.g., failure to obtain informed consent or failure to obtain informed consent prior to study entry); randomization errors; failure to report SAE's, unanticipated adverse device effects, and deaths within applicable regulatory timeframes; device accountability issues (e.g., missing or lost investigational product); or device misuse / unauthorized device use.
- Minor deviation: Deviation from a protocol requirement such as incomplete/ inadequate subject testing procedures, non-compliance with medication regimens, follow-ups performed outside specified time windows, etc.

The Sponsor will monitor continuously monitor site compliance. The site will receive a list of site-specific study deviations on an annual basis as part of the Annual Progress Report and as part of the Final Report upon completion of the study.

#### 12.5 DATA MONITORING COMMITTEE (DMC)

A Data Monitoring Committee (DMC) will provide ongoing independent review and adjudication of study endpoint events, the safety data, further ensuring the continued safety of subjects, as well as the validity and scientific merit of the trials. The DMC consists of at least three voting members, with relevant expertise. The DMC members are not directly related to the study.

### **13 DEVICE ACCOUNTABILITY**

All medical devices used in this clinical study carry a CE mark and will be used within their intended use. Therefore, this study does not require a dedicated device accountability procedure. The investigator shall maintain adequate records of the receipt and disposition of all devices per local institutional standard practice and regulations.

## **14 PROTECTION OF HUMAN SUBJECTS**

### **14.1 STATEMENT OF COMPLIANCE**

This study will be conducted in compliance with the current ICH E6 GCP, the ethical principles of the Declaration of Helsinki, current FDA GCP guidelines, and any additional national or EC or CA-required procedures, whichever represents the greater protection for the individual.

### **14.2 INFORMED CONSENT**

This study will be conducted in compliance with current ICH E6 GCP pertaining to informed consent. To participate in the study, the subject must sign and date the ICF after having been informed about the nature and purpose of the study, participation and termination conditions, risks, and benefits, before initiation of any study-related procedures. A copy of the signed ICF must be provided to the subject. If applicable, the ICF will be provided in certified translation for non-English-speaking subjects. Signed ICFs must remain in the subjects' study files and be available for verification by the Sponsor or Sponsor representative at any time.

## 15 STATISTICAL CONSIDERATIONS

### 15.1 GENERAL ANALYSIS PRINCIPLES

All primary endpoint analyses will be conducted under the principle of "Intention-To-Treat" (ITT), where each subject randomized to a treatment group who has had a mapping and/or ablation catheter inserted shall be considered part of the ITT group. As a secondary exploratory analysis, a "Per Protocol" (PP) analysis may be performed with a subgroup of the ITT group who have no major protocol deviations reported.

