**Table 5 – Intra-Procedure Guidelines**

Parameter	Description
-----------	-------------

Vascular access	Under sterile technique, the right and/or left femoral veins may be cannulated via Seldinger, or percutaneous approach. Other vascular access also may be obtained based upon physician judgment.
Reference catheter placement	Reference catheters (including 64-pole FIRMap catheter(s)) may be inserted and placed within the heart to record signals as clinically required at the discretion of the physician.
Access to left atrium	Access to the left atrium should be made according to the institution's standard practice.
Anticoagulation	Heparin should be administered per local protocol in order to achieve and maintain ACT > 300 prior to insertion of FIRMap catheter, if applicable. Heparin should be administered immediately following transeptal puncture in the case that ACT is not >300.
Catheter placement	Catheters may be inserted and used according to the institution's standard practice.
Source arrhythmia diagnosis	For FIRMap patients only: After obtaining at least 1 minute of continuous electrograms from the 64-pole FIRMap catheter either simultaneously or sequentially in the right and left atria, these electrogram data will be transferred to the RhythmView system. Right atrial mapping will initially be performed. If no right atrial rotor/source is detected or all right atrial rotors are eliminated, left atrial mapping will be performed. This will then produce FIRMap displays which will be interpreted by the operator to determine which locations have focal or rotor rhythms that could be sources of the AF.
3-D Electroanatomic Mapping	3-D electroanatomic maps may be created using CARTO (Biosense Webster, Johnson & Johnson) or Nav-X (St. Jude Medical) systems for documentation of anatomy and ablation lesion locations.
Induction of sustained AF	If the patient is not experiencing spontaneous, sustained AF (>5 min uninterrupted), induce sustained AF by atrial burst pacing from a catheter positioned within the CS or left atrial appendage until the atrial refractory period is reached or AF is induced with or without isoproterenol infusion.  IF AF CANNOT BE SUSTAINED, THE PATIENT DOES NOT MEET THE INCLUSION CRITERIA FOR THE PROTOCOL AND THE PATIENT WILL UNDERGO CONVENTIONAL AF ABLATION PER PHYSICIAN DISCRETION.

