### C. *Intra-procedure Measurements*

The following data will be collected during the procedure. Table 6.

Data	Description
Fluoroscopy times	To be recorded: Total fluoroscopy time 
 
● The total fluoroscopy time for the procedure (a.k.a., "pedal down" time)
 

Total RF ablation time	Total RF ablation time as measured by total time of ablation lesion applications, from first ablation lesion to end of last lesion, will be documented. These values will be noted in both the FIRM-guided and conventional ablation groups. If ablation for AT/atrial flutter is pursued, this ablation time will be documented separately
Total procedure time	Total procedure time defined as: time from insertion of first sheaths for vascular access to removal of sheaths.
Medication administration	Cardiac medications administered during the procedure including drug name, dosage, and indication and will be recorded.
Devices and equipment	Devices and equipment used during the procedure including access devices, diagnostic and ablation catheters, and mapping equipment type will be recorded.

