#### C. Long-Term Secondary Safety (safety endpoint)

Long-term safety is defined as freedom from serious adverse events related to the procedure (including those related to repeat procedures) within one year of the index procedure.

---

 Dukkipati, Srinivas R. MD, et. al. (2015). Pulmonary Vein Isolation Using the Visually Guided Laser Balloon. Journal of the American College of Cardiology. 66(12):1350-1360.

The statistical hypothesis for this endpoint is operationalized as follows:

$H_0: p_F = p_C$

$H_A: p_F \neq p_C$

$\alpha = .05$  (two-tailed)

Where:

$P_F$  = the proportion of subjects free from serious adverse events related to the procedure (including those related to repeat procedures) within one year of the index procedure in the FIRM-guided ablation arm

$p_C$  = the proportion of subjects free from serious adverse events related to the procedure (including those related to repeat procedures) within one year of the index procedure in the conventional ablation control arm

The proportion of successes in each treatment arm shall be estimated using Kaplan-Meier survival estimation.

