#### D. Acute Safety (Secondary safety endpoint)

The acute safety success of either treatment arm is defined as freedom from serious adverse events related to the procedure within seven (7) days of the index procedure.

The proportion of successes in each arm will be calculated as follows:

$$\frac{n}{N}$$

Where:

$n$  = the total count of subjects presenting freedom from serious adverse events related to the procedure within seven (7) days of the index procedure.

$N$  = the total count of subjects in that arm in the ITT group

The statistical hypothesis for this endpoint is operationalized as follows:

$H_0: p_F = p_C$

$H_A: p_F \neq p_C$

$\alpha = .05$  (two-tailed)

Where:

$P_F$  = the proportion of "successes" in the FIRM-guided ablation arm

$p_C$  = the proportion of "successes" in the conventional ablation control arm

The analysis to be performed for this endpoint will be a Chi-square test of Independence.

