## 2 Statistical Methods

### 2.1 General Analysis Principles

All primary endpoint analyses will be conducted under the principle of “Intention-To-Treat” (ITT), where each subject randomized to a treatment group who has had a mapping and/or ablation catheter inserted shall be considered part of the ITT group. As a secondary exploratory analysis, a “Per Protocol” (PP) analysis may be performed with a subgroup of the ITT group who have no major protocol deviations reported.

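### The acute safety denominator admits only subjects who had a mapping or ablation catheter inserted, so a serious access complication that ends the procedure before that step is not counted

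*Protocol*

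**What the plan says.** **Analysis group.** Protocol 15.1 defines its ITT group as follows: "each subject randomized to a treatment group who has had a mapping and/or ablation catheter inserted shall be considered part of the ITT group". SAP 2.1 repeats the rule: "who has had a mapping and/or ablation catheter inserted shall be considered part of the ITT group". The sentence that introduces it limits its scope: "All primary endpoint analyses will be conducted under the principle of" ITT. Neither document defines a separate safety set.

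**Acute safety.** Protocol 15.2 D calls this secondary and computes n/N, where N is "the total count of subjects in that arm in the ITT group". SAP 2.2.3 uses the same denominator.

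**Long-term safety.** Protocol 15.2 C and SAP 2.2.4 name no population and give only the estimator: "The proportion of successes in each treatment arm shall be estimated using Kaplan-Meier survival estimation". The protocol lists the endpoint as secondary (Table 2 and 15.2 C). The SAP lists it under Primary Outcomes (1.2.1) and calls it primary in 2.5 and 2.6.

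**Order of events.** Randomisation follows the baseline assessments (Protocol 7.4), before the procedure. Total procedure time is "time from insertion of first sheaths for vascular access to removal of sheaths" (Protocol 9.2 C). Protocol Table 8 notes: "Left heart access via trans-septal puncture has known potential adverse events of: cardiac perforation, cardiac tamponade, and embolic events", and its footnote puts that risk below 1%. In the FIRM arm, "Right atrial mapping will initially be performed" (Protocol Table 5).

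**The concern.** A subject is exposed to procedural risk from the first sheath, but enters the acute safety analysis only when a qualifying catheter is inserted. A complication in that interval can itself prevent the insertion. Membership of the analysis set then depends on the outcome being measured, and the excluded cases are serious by construction, since the event was bad enough to stop the procedure.

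Comparing safety is part of the primary objective (Protocol 4). A tamponade at trans-septal puncture that ends the case before any qualifying catheter is placed is plainly a procedure-related SAE within 7 days. Under the written rule it appears in neither n nor N.

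**Working it through.** **Step 1. Which subjects are lost from acute safety.**

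| Course after randomisation | In the ITT group? | SAE counted? |
|---|---|---|
| Access complication, catheter inserted afterwards | Yes | Yes |
| Complication after catheter insertion | Yes | Yes |
| Access complication, procedure abandoned before any mapping or ablation catheter | No | No |

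Only the third row is affected.

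**Step 2. Whether another rule restores them.** SAP 2.5 gives two presentations for subjects with missing acute data or lost to follow-up. It does not add subjects who are outside N. SAP 2.5.1 foresees subjects failing entry criteria after randomisation, possibly during the procedure, but assigns them to no safety set, and its minimum data list does not name adverse events. The adverse event tables in SAP 3.1 state no population and are not the endpoint test.

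**Step 3. Arm size.** The plan gives no figure for safety. Its arm size comes from the effectiveness endpoint, with rates .50 and .55, margin .15, one-sided 5% and 80% power:

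n = (1.645 + 0.842)² × (0.50×0.50 + 0.55×0.45) / (0.15 + 0.05)² = 6.18 × 0.4975 / 0.04 = 76.9, so 77 per arm; 77 × 1.10 = 84.7, so 85.

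This matches the stated 77 and 85. It does not bear on the concern beyond supplying 85.

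**Step 4. Expected loss per arm.** Let r be the rate of procedure-related SAEs that end the procedure before a qualifying catheter. The documents do not give r. Their only figure is the bound of under 1% for trans-septal events, so r = 1% is a ceiling for that component. The other rows are assumptions. The documents give no rate for sheath-site events, and the 2% row shows a higher combined rate.

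Expected loss = 85r; P(at least one) = 1 − (1 − r)^85.

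| r | Expected lost | P(at least one) |
|---|---|---|
| 0.2% | 0.17 | 16% |
| 0.5% | 0.43 | 35% |
| 1% (trans-septal ceiling) | 0.85 | 57% |
| 2% | 1.70 | 82% |

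**Step 5. Effect on the endpoint.** Assume 4 other SAEs in each arm of 85 (an illustration, not a figure from the documents). The p values are uncorrected chi-square tests against 4/85 in the other arm.

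- One subject lost: 5/85 = 5.9% with everyone counted, 4/84 = 4.8% under the catheter rule, a shift of 1.1 points. p = 0.73 against 0.99.
- Two lost: 6/85 = 7.1% against 4/83 = 4.8%, a shift of 2.2 points. p = 0.51 against 0.97.

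With 2 or 6 other SAEs instead of 4, losing one subject shifts the rate by 1.15 or 1.09 points.

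**The case against.** **The events stay visible.** Adverse events are assessed at the procedure (Protocol Table 4), SAEs go to the sponsor within 24 hours (10.2), the DMC reviews safety data (12.5), and SAP 3.1 and 3.2 plan tables and listings with no stated ITT restriction. This stands: safety oversight is not blind to these cases. It does not change the endpoint, whose denominator is explicit.

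**Few subjects, unpowered endpoint.** This also stands. Only effectiveness was powered, and the illustration above changes no conclusion.

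**The loss falls mainly on control.** A reader might infer this because FIRM mapping starts in the right atrium, so FIRM subjects could already qualify when the septum is crossed, while control work is in the left atrium. The documents do not establish it:

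- The ACT row of Protocol Table 5 allows either FIRMap insertion or trans-septal puncture to come first.
- The mapping row of that table allows simultaneous recording in both atria.
- Reference catheters are not restricted to one arm, and both arms may need a coronary sinus catheter to induce AF.
- Neither document says whether such a catheter counts as a mapping catheter.

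If the asymmetry were real, it would make control look safer and so work against FIRM. Loss during sheath access can occur in either arm.

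**Both safety endpoints carry the rule.** This is explicit only for acute safety. For long-term safety it follows only by combining the SAP's primary label with the ITT sentence. Under the protocol, where the endpoint is secondary, the population is left open.

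**Conclusion.** The point holds in a limited form. For acute safety, the written denominator leaves out any subject whose procedure-related SAE ends the procedure before a mapping or ablation catheter is inserted. This is a stated rule that gives a wrong count, not merely a missing detail. For long-term safety, the population is unnamed and the two documents disagree on whether the endpoint is primary.

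The size is small. Trans-septal events would remove fewer than 0.85 subjects per 85, with at most a 57% chance of removing any, and each removal shifts the arm's rate by about 1.1 points. These are upper limits for that component, because they assume that every such event ends the procedure before catheter insertion. Sheath-phase losses would add to this at a rate that the documents do not give.

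Two larger readings go too far. Access complications as a class do not leave the count, because those followed by catheter insertion remain in it. Nor do the documents support a claim that a large share of control SAEs could vanish. Dividing 0.85 by an assumed 1.7 to 4.25 events per arm (2% to 5% of 85) gives 50% to 20%, but neither document states an SAE rate, and the ratio takes the worst case at every other step.

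**What to change.** In Protocol 15.1 and SAP 2.1, add a safety set: all randomised subjects in whom the procedure was started, meaning that the first sheath was inserted. Then:

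- Use it as N for acute safety (Protocol 15.2 D, SAP 2.2.3).
- Name it as the population for long-term safety (Protocol 15.2 C, SAP 2.2.4).
- Give safety the same primary or secondary status in both documents.
- State that subjects in this set stay in adverse event follow-up to 12 months, including those classed as screen failures after randomisation.

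First sheath insertion suits this purpose because it already starts the recorded procedure time. Start of sedation is not among the measurements listed in Protocol 9.2 C. The new set also makes the undefined term mapping catheter irrelevant to the safety analysis.

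The cost is a few sentences in each document, a check that the case report form records sheath insertion for abandoned cases, and continued follow-up of the few subjects concerned. The effectiveness analysis and the sample size do not change.
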